5.2 Subject Exclusion Criteria

Providers not able or willing to record current tobacco use status in their EHR are not eligible. Private practice providers must not be affiliated with the engaged dental schools (Indiana University or University of Pittsburgh) in a teaching or clinical position.

Patient exclusion criteria applied to the usual care post-index encounter telephone screening include: (a) patients requesting to opt out of research.

5.3 Strategies for Recruitment and Retention

Recruitment and retention of providers: Associated dental hygienists and dentists working in private practice settings, and predoctoral and dental hygiene students will be recruited to the trial using informational handouts and personal communication with study staff. Private practice practitioners will be recruited through existing relationships of the National Dental PBRN or the institutions involved in the project. Dental school students will be recruited through on-site information sessions conducted by non-faculty.

Dental schools: The School of Dental Medicine at the University of Pittsburgh and the Indiana University School of Dentistry will recruit student participants through the dental school predoctoral and DH clinics. Information sessions hosted by the appropriate project staff will be held at each dental school. Information about the study will be presented at that time and any potential questions by students will be answered by study project management staff with no relationship to the students. Study staff with no academic relationship to student providers will administer consent in accordance with IRB-approved site-specific procedures.

Private practices: The study team will recruit private practice clinics through relationships established in the National Dental PBRN and prior studies by the investigators at the academic institutions represented. Midwest Regional Coordinators

who are jointly study staff have relationships with practitioners and can answer questions about the study and about participation in research in general, and further support the involvement of interested practitioners. No additional National Dental PBRN resources will be used. Study staff can use administrative databases and Network enrollment questionnaire data to identify eligible private practice settings.

Provider incentives: Incentives will be provided to students per policy of the school. Private practice providers will receive incentives at the completion of the study. All providers will receive a free CE session with a web-based video course on the current US Department of Health and Human Services: *Treating Tobacco Use and Dependence: 2008 Update—Clinical Practice Guideline*.

Recruitment and retention of patients: We anticipate based on administrative data to achieve cumulative consecutive patient enrollment across sites to total 1,440 in 8 or fewer months (site specific). Patients who have authorized secondary disclosure of their information will be securely transferred to HealthPartners. Only study-eligible patients will be contacted by the SRC. Patient contact data and encounter details will be reported daily using an EHR system routine (to be programmed by vendor).

To facilitate surveys, verbal consent will be obtained for patients contacted by phone within 7 days of their index visit. Consent and surveys will be conducted centrally by SRC professional telephone interviewers trained in human subjects' protection, HIPAA for research and the Responsible Conduct of Research. Patients will be called up to eight times at various times of day, including evenings, and days of the week, including Saturdays, to maximize recruitment and opportunities for follow-up.

Patient participants will be provided an incentive after completion of the baseline and 6-month survey.

5.4 Treatment Assignment Procedures

Dental school predoctoral/dental hygiene clinics in Indiana and Pennsylvania, and private practice clinics will be randomized. All consented providers and their patients will be allocated to the study arm to which their clinic is assigned.

5.4.1 Randomization Procedures

Within the predoctoral and dental hygiene clinics, clinic modules will be randomized to study arm using covariate-based constrained randomization. Balancing covariates will be specified in the final Statistical Analysis Plan. Private practice clinics will be randomized to study arm using covariate-based constrained randomization. Balancing covariates will include factors that are measurable across all clinics in the recruitment pool. Clinic-level factors to be considered include number of patient visits, number of smokers, percentage of patients who are smokers, percentage of patients with public-pay insurance, percentage in specific age groups. The final randomization plan and balancing covariates will be described in the final Statistical Analysis Plan.

5.4.2 Masking Procedures

Neither the CDS- nor the control-study arms in dental school and private practice clinics will be masked. Study staff will know which clinic assignment, and providers will know clinic assignment due to the obvious presence or absence of clinical decision support available within the EHR at each clinic. Some protection from bias occurs due to patients not being aware that a study is occurring until they are contacted by research staff following their index visit. Patients are not made aware of the study arm to which their clinic is assigned. However, provider knowledge of study arm could be relayed by providers during the dental visit. The Survey Research Center interviewers conducting the evaluation interviews will be blind to the patient's clinic assignment.

5.5 Subject Withdrawal

Participants may withdraw voluntarily from the study or the investigator may terminate participation.

5.5.1 Reasons for Withdrawal

Subjects are free to withdraw from participation in the study at any time upon request. Patients or providers may wish not to participate due to the perceived impact on their time or privacy. Incomplete surveys will be counted as withdrawals.

5.5.2 Handling of Subject Withdrawals or Subject Discontinuation of Study Intervention

Patient withdrawal. Within the parameters prescribed by the study protocol, study staff will provide support and encouragement to participants in order to minimize withdrawal and attrition during the intervention. Every effort will be made to undertake protocol-specified safety follow-up procedures and capture adverse events (AEs), serious adverse events (SAEs), and unanticipated problems (UPs).

Patients may elect to withdraw at any time with no impact on their relationship with their provider or the institutions involved on conducting the research. With respect for both patients and providers, refusal conversion will not be attempted. Respondents may actively or passively refuse to participate in the evaluation surveys. Active refusals will not be contacted again by the Survey Research Center. Passive refusals (i.e., a subset of non-responders) will only be contacted up to a maximum number of email (providers) or telephone (patient) attempts (up to 8) to be respectful of participants and within bounds of IRB approval. Withdrawal of providers will be tracked in the provider database by the project manager. Withdrawal of patients will be tracked by the SRC staff in the centralized study database.

Withdrawn patients will not be replaced. In the case of patient withdrawal from the study, staff will only attempt continued follow-up data collection for patients who are withdrawn due to an unanticipated problem (UP). In those cases, only data related to the completion of reporting requirements for the UP will be recorded. Patients withdrawn from the study for any other reason will have the date and reason for withdrawal

recorded (if known), but will not have any additional study data recorded. Although patients withdrawn from the study may continue to receive normal clinical care as patients of the participating dentists, additional study data will not be collected from this continuing clinical care (except as noted above).

Practitioner withdrawal. Withdrawn private practices will be replaced with a suitable alternate clinic until the time of randomization ensuring covariate balance remains intact.

5.6 Premature Termination or Suspension of Study

This study may be suspended or prematurely terminated if there is sufficient reasonable cause. Written notification, documenting the reason for study suspension or termination, will be provided by the suspending or terminating party. If the study is prematurely terminated or suspended, the principal investigator will promptly inform the IRB and will provide the reason(s) for suspension or termination.

Circumstances that may warrant termination include, but are not limited to:

- Determination of unexpected, significant, or unacceptable risk to subjects.
- Insufficient adherence to protocol requirements.
- Data that are not sufficiently complete and/or evaluable.
- Determination of futility.

6 STUDY INTERVENTION

6.1 Study Behavioral or Social Intervention(s) Description

A user-centered design of the CDS tool is supported by prior multi-method approaches of the study team which have explored tobacco cessation activities and EHR workflows among dentists and dental hygienists. Each patient-specific index visit for the study is defined as the first encounter during the clinic-specific implementation period when the enrolled provider updates that patient's smoking status in the CDS application, cueing contact by the Survey Research Center (SRC). Additional subsequent dental visits may include additional CDS updates by the provider, but these encounters do not result in additional SRC contacts until the 6 month patient survey.

Prior research supports CDS that should not interrupt the providers' usual approach to history taking. Thus a user-centered approach to activation of the CDS will allow for a seamless integration into a variety of practitioner workflows (e.g., dental hygienists' versus dentists' workflow) and visit types. This integration will enable providers to engage the CDS whenever a tobacco cessation is relevant to the patient encounter. Our prior work has shown the merit of this approach (64).

Provider scripts and patient educational materials are based on the current clinical practice guideline endorsed by a consortium of eight Federal Government and nonprofit organizations, AHRQ's evidence-based guidance materials for healthcare providers, and materials available to patients from <http://smokefree.gov/>. Script flow is based on the 5As model (Ask, Advise, Assess, Assist, Arrange). Supportive motivational intervention messaging is provided for patients not ready to make a quit attempt now.

6.2 Administration of Intervention

The EHR vendors will modify their respective EHR products to integrate the CDS. After pilot testing, this modified EHR product will be installed in all study and control clinic environments and exposed to consented dental providers (dentists, dental students, dental hygiene students).

In the context of the familiar EHR environment, providers in the intervention arm will be exposed to the CDS. Assessment of the patients' reported daily use, previous quit attempts, and interest in quitting drives a CDS rule-based algorithm that displays personalized scripts for that patient. Using the scripts as a jumping off point, the provider is free to adapt the messaging using best clinical judgment and according to patients' individual needs and preferences as well as risk factors for oral disease (see Section 6.3 on observational monitoring of fidelity for details about evaluating standardization of the delivery of the scripts as intended per the clinical guideline). The provider selects scripts and patient resources that were "delivered." Using this information, the tool creates an automated "smart note" to efficiently document the activities for reference in guiding future encounters, as well as for compliance with record keeping requirements.

6.3 Procedures for Training Interventionists and Monitoring the Quality of the Provider Behavior Measures

Procedures for Training Interventionists Providers in private practices in both the intervention and control clinics will participate in a video-cast professional CE course (approximately 30 minutes) on how to implement the current tobacco cessation guideline, specifically in dental practice. The two dental schools participating in this study place a high priority on comprehensive guideline-driven tobacco education. All students are exposed to tobacco cessation training in their curriculum, however it occurs early in the didactic curriculum, so students will also view the video-cast thus standardizing, as much as is practical, their most recent knowledge with practicing providers. All intervention clinics will receive basic training on the functionality of the CDS tool in the form of a video-cast and an interactive session with a project manager who has clinical training experience.

Monitoring Provider Behavior Measures Utilizing Clinic Observations

The outcome measure for Objective 1 relies on patient reporting of the provider actions during the clinical encounter. This measure has the potential for inaccurate recall by the patient. To address this concern we will conduct observations on a subset of the clinical encounters, recording the actions of the provider. These results will be compared to the patient reported results in order to determine the degree of recall bias. The number of observations will be determined after assessing agreement of the two measurements.

6.4 Assessment of Subject Compliance with Study Intervention

The HPI data center will generate reporting tools summarizing patient response rates. These reports will be provided to the study team and reviewed monthly to determine the need for additional training. This report will be reviewed monthly by the study team and by the Medical Monitor as needed.

6.5 Study Procedural Intervention(s) Description

A user-centered design of the CDS tool is supported by prior multi-method approaches of the study team (52) which have explored tobacco cessation activities and EHR workflows among dentists and dental hygienists. Based on this preliminary work and responses to a survey of National Dental PBRN members from across the US, the CDS will be designed to target specific index visits (D0140. Limited oral evaluation; D0150. Comprehensive Oral Evaluation) when it is expected the dentist and/or dental hygienist will routinely update the patient's medical history and smoking status. In the intervention clinics the CDS will be activated when the tobacco status is updated. A flexible approach to accessing the tool will allow for adaptability to a variety of practitioner workflows and visit types and will enable providers to engage the CDS when relevant to the patient encounter.

Provider scripts and patient educational materials are based on the current Clinical Practice Guideline sponsored by a consortium of eight Federal Government and nonprofit organizations (55), AHRQ's evidence-based guidance materials for healthcare providers (56), and materials available to patients from <http://smokefree.gov/>. Script flow is based on the 5As model (Ask, Advise, Assess, Assist, and Arrange). Supportive motivational intervention messaging (57) is provided for patients not ready to make a quit attempt now.

Figure 1 of the Visualization Appendix (Appendix E) illustrates the three parts of the CDS as it appears within the providers' EHRs. The provider asks a few tobacco questions about smoking status as part of a health history update that triggers the CDS. The interventions delivered by the provider are customized based on the smokers' responses to baseline questions. The provider elects which personalized scripts and patient resources to deliver in the patient encounter by checking the boxes provided. Using this information, the tool creates an automated "smart note" to efficiently document the activities and for use in follow-up during future encounters with the patient. This figure also illustrates the CDS functionality which generates unique script sets based on the patient's smoking status (i.e., reported daily use), previous quit attempts, and interest in quitting.

6.6 Administration of Procedural Intervention

See study Manual of Procedures (MOP) for this detail.

6.7 Procedures for Training of Clinicians on Procedural Intervention

See site-specific training materials (MOP appendix) for this detail.

6.8 Assessment of Clinician and/or Subject Compliance with Study Procedural Intervention

See study MOP monitoring plan for this detail as well as Section 14 on quality control and quality assurance.

7 STUDY SCHEDULE

7.1 Screening

Providers: To ensure students meet inclusion criteria, they will attend a lunch and learn session at which time informed screening, recruitment, and consent procedures will be completed with study staff who do not have a relationship with the students (e.g., no academic oversight).

Patients: Providers will routinely assess patients for tobacco status. Patients who have authorized secondary disclosure of their information will be securely transferred to HealthPartners. Only study-eligible patients will be contacted by the SRC.

7.2 Enrollment/Baseline

Provider baseline enrollment: Providers in private practices may be enrolled in dentist/dental therapist/dental hygienist, as appropriate, since care is delivered as a team. Dental and dental hygiene students will be enrolled as individuals nested within clinic modules that are anticipated to be static for the duration of the study period. Upon enrollment, providers and student providers will be invited to complete the baseline survey.

Patient baseline enrollment: Study enrollment and all follow-up data are driven by the index visit. A system-generated, study specific-encounter ID will ensure patients are only contacted at baseline one time, even if intermediate dental encounters occur and their tobacco status is updated again.

7.3 Intermediate Visits

Patient intermediate visits: Not applicable. Patients may return for non-study related dental visits. These visits will not alter the timeline of the baseline or 6-month follow-up surveys

Provider intermediate visits: Not applicable. Providers are surveyed at baseline and after 6 months of study participation.

7.4 Final Study Visit

Patient final visits: The final patient contact consists of the SRC-administered 6-month survey conducted by phone and tracked in the central REDCap database.

Provider final visits: The final provider visit consists of the 6-month survey administered electronically and tracked in the central REDCap database.

7.5 Withdrawal Visit

Patient withdrawal: Patients may withdraw at any dental visit within the study period. This will be relayed by the dental provider and tracked by the project manager or SRC staff such that follow-up is discontinued. This option will be addressed with providers in

training. Patients may also withdraw while in contact with SRC staff. This will not affect nor be communicated to providers, practices, or schools.

Practice withdrawal: Up to 4 back-up private practices will be recruited to accommodate clinic-level withdrawal. Withdrawn private practices will be replaced with a suitable alternate clinic to ensure clinic randomization remains intact.

7.6 Unscheduled Visit

No unscheduled intervention-related visits are anticipated. Unscheduled contact may occur with the study manager whose contact information will be provided (e.g., patients seeking clarification about incentive payment). This is common and typical in practice-based research which takes a customer-service based approach to ensuring participants have comfort with and ease of accessibility to the researchers.

8 STUDY PROCEDURES /EVALUATIONS

8.1 Study Procedures/Evaluations

Patient Survey procedures: Patient contact data will be sent to the HPI Survey Research Center in keeping with HIPPA authorization procedures and Data Use Agreements approved by the respective sites. In the period between 1-7 days after the index dental visit, a baseline survey will be attempted with each patient. Call attempts continue until either a survey is completed or a patient indicates that they do not want to participate. The outcome disposition of each call attempt is recorded by the interviewer in the centralized study database to ensure accurate calculation of contact, response, cooperation and refusal rates. Upon successful contact with a patient, interviews will be conducted with willing participants in a standardized manner utilizing the IRB approved script and survey questions and responses. Refusal conversion is not attempted. Any study-related patient questions are fielded using a study Frequently Asked Questions document. Survey responses are recorded by the interviewer in real-time in the centralized study database. Interviewers are monitored for script adherence, accuracy of data entry and study knowledge by SRC staff.

Patients that complete a baseline survey become due for a follow-up survey six months after the index visit. In order to maximize response rates, the SRC will begin calling these patients one-week before the six-month mark. Up to eight call attempts will be made in the two-week window spanning the six-month mark. Call attempts, survey administration and documentation follow the same procedure as the baseline survey. Survey questions vary slightly between the baseline and six-month surveys as indicated in the Survey Item Grid (Appendix K).

Interviews will be conducted in English and Spanish. The IRB approved script and questionnaire will be translated, back-translated and reconciled by a professional translation firm. Spanish-speaking trained telephone interviewers, employed by the SRC, will attempt survey completion with Spanish-speaking patients. All interviewers work onsite in a central location. In addition to completion of training in practices of standardized telephone interviewing for research, all interviewers are trained in HIPAA and the responsible conduct of research through CITI.

Provider survey procedures: Upon enrollment in the study, providers will receive their baseline survey. Private practice providers will be asked to complete and return theirs by the completion of the training session. Student providers will be invited to complete theirs in the lunch and learn session where the study is introduced. Survey responses will be collected separately from any identifiers (e.g., provider ID) needed to connect provider data to clinic level data for the purposes of analysis. Six-month surveys (90 days -30/+90 days) will be provided and collected confidentially by the project staff at the respective sites. HealthPartners project managers will deliver and obtain surveys from the private practice settings. Baseline and 6-month surveys will be marked with a common study ID.

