Population:	
• Practitioners. Up to 88 dental hygienists and 88 dentists working in up to 22 private practice settings and 360 predoctoral and 65 dental hygiene students in two dental schools will be recruited to the trial.• Patients. 720 adult smokers with routine dental visits in dental school settings and 720 adult smokers with routine dental visits in private practice settings seen by practitioners enrolled in the trial are eligible for enrollment in order to achieve 430 completed surveys in each setting.
Phase:	Phase 3 clinical trial
Number of Sites:	
This study will be conducted in up to 14 clinic modules within two dental school programs and 22 private practice clinics.
 
The School of Dental Medicine at the University of Pittsburgh (Pitt) and the Indiana University School of Dentistry (Indiana) have been selected as study sites for this project based on their emphasis on teaching smoking interventions as part of their predoctoral and dental hygiene (predoc/DH) curriculum.
 
Up to 22 private-practice clinics having 1-5 dentists and 1-10 hygienists will be engaged by recruiting volunteers convenience sampled from dentists and dental hygienists participating in the National Dental PBRN or otherwise recruited through existing relationships with HealthPartners, the University of Pittsburgh, and Indiana University.

Description of	The intervention is dental provider exposure to an HIT-driven

Intervention:	CDS tool. The CDS tool generates evidence-based, guideline-driven provider script sets to assist in the delivery of cessation support to smoking patients. A rule-based algorithm personalizes the scripts to account for patients' current smoking status and interest in quitting. A user-centered design approach underpins the CDS tool design that is expected to be delivered in 2 - 5 minutes to remain feasible among the management of multiple priorities in the patient encounter. Provider training will be composed of two components: 1) Clinical practice guideline knowledge (intervention and control clinics) and 2) CDS functionality (intervention clinics only).
Study Duration:	60 months

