Provider sex	Male or female	Provider survey (baseline)	Nominal
Provider race	Standard categories	Provider survey (baseline)	Nominal
Provider years in practice	Years	Provider survey (baseline)	Interval
Provider type	Dentist or hygienist	Provider survey (baseline)	Nominal
Provider TDQ individual domain scores	Proposed moderators in Aim 3 (Objective 4) analyses: Theoretical Domain Questionnaire individual domain scores (10 total)	Provider survey (baseline)	Ordinal
Change in provider self-efficacy TDQ individual scores from baseline to 6 months	Proposed mediators in Aim 3 (Objective 4) analyses: Self-efficacy items from Theoretical Domain Questionnaire	Provider survey at baseline and 6 months after intervention	Ordinal
Provider satisfaction with CDS	Provider ratings of satisfaction and usability of CDS	Provider survey 6 months after intervention	Ordinal

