15.2 Data Capture Methods

Data Collection. There are four main data instruments for the study: 1. The patient baseline telephone survey conducted 1-7 days after the index dental encounter, 2. The patient 6-month post-baseline telephone survey, 3. The provider survey conducted both pre- and post-implementation, and 4. The instrument used to monitor general adherence to the use of the CDS tool as intended.

Screening. Demographic and tobacco status information verified at the time of the encounter will be used for determining patient eligibility

CDS Data. Tobacco assessment details and documentation of use of SBIRT scripts and patient resources used by providers will be collected electronically at the point of care through a secure web application.

Data collection and accurate documentation will be the responsibility of all study staff under the supervision of [name] and [name], the co-PIs. Unanticipated problems and adverse events will be reviewed by the investigator or designee.

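### Protocol 8.1 accepts private-practice baseline surveys up to the end of training, so the starting scores for exploratory Objective 4 may already reflect training

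*Protocol*

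**What the plan says.** **Timing.** Protocol 8.1 begins with a rule for everyone: "Upon enrollment in the study, providers will receive their baseline survey". Section 7.2 likewise invites providers to complete it on enrollment. Section 8.1 then separates the settings. For private practices, "Private practice providers will be asked to complete and return theirs by the completion of the training session". For students, "Student providers will be invited to complete theirs in the lunch and learn session where the study is introduced". Section 15.2 lists the instrument as "The provider survey conducted both pre- and post-implementation".

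**Training.** The Protocol Summary gives provider training two components: "1) Clinical practice guideline knowledge (intervention and control clinics) and 2) CDS functionality (intervention clinics only". Section 6.3 adds detail. On the guideline part, "Providers in private practices in both the intervention and control clinics will participate in a video-cast professional CE course", lasting about 30 minutes. On the tool, "All intervention clinics will receive basic training on the functionality of the CDS tool in the form of a video-cast and an interactive session".

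**Use of the scores.** Table 2 in section 3.3 names the ten baseline Theoretical Domain Questionnaire (TDQ) domain scores as proposed moderators for Objective 4. It names as proposed mediator "Change in provider self-efficacy TDQ individual scores from baseline to 6 months".

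**The concern.** A baseline score used in a moderation or mediation analysis should precede the exposure. The private-practice rule does not ensure this. A provider can answer self-efficacy items after being taught how to counsel smokers and, in an intervention clinic, possibly after being shown the tool.

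Two things are at stake. A change score that starts after training omits whatever was gained in training. A moderator that the assigned arm has already shifted is no longer a pre-exposure characteristic, so an interaction with arm could be created or hidden. Neither fault can be fully repaired in the analysis once the survey has been taken late.

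**Working it through.** The plan states no self-efficacy effect, standard deviation or power for Objective 4, so there is no figure to reproduce. The check compares the text and then works through an illustration with assumed values.

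**1. Does any rule put the survey before training?**
- Sections 8.1 and 7.2 issue the survey at enrollment. Early completion is possible but not required.
- Section 8.1 makes the end of the training session the return limit for private practices.
- Section 15.2 requires it before implementation. A survey returned at the end of training can still meet that.
- SAP section 3 randomizes private practices as they become eligible, without placing randomization relative to survey or training.

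No rule closes the gap. Students are invited at the introductory session, with no link to training. SAP section 3 balances school modules on the number of consented students, which suggests that consent comes before randomization there. The late limit is specific to private practices.

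**2. Can the effect differ by arm?** Training in CDS functionality is given in one arm only, so it must follow assignment. If the training session in 8.1 includes that part, a compliant survey can follow arm-specific exposure. If it means only the guideline course, the content is common to both arms.

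**3. Effect on the mediator.** Let:
- A = the arm-specific self-efficacy gain by 6 months;
- s = the share of A that arises at training;
- g = the gain from guideline training, equal in both arms;
- f = the share of intervention-arm private-practice providers who answer after training, first taken to be the same in the control arm.

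The late baseline absorbs f(g + sA) in the intervention arm and fg in the control arm. The between-arm contrast in mean change is therefore

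A − f(g + sA) + fg = A(1 − s·f).

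The guideline term cancels. It would leave a residue only if the late share differed by arm: (f_I − f_C)·g, where f_I and f_C are the late shares in the intervention and control arms.

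Contrast kept, all s and f assumed:
- s = 0.25, f = 0.5: 1 − 0.125 = 87.5%
- s = 0.5, f = 0.5: 1 − 0.25 = 75%
- s = 0.5, f = 1: 1 − 0.5 = 50%
- s = 1, f = 1: 0%

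For scale only, take a contrast with 80% power at full size (two-sided alpha 0.05). If a fraction r is kept, power is Φ(2.802·r − 1.960), where 2.802 = 1.960 + 0.842:
- r = 0.875: Φ(0.49) = 69%
- r = 0.75: Φ(0.14) = 56%
- r = 0.5: Φ(−0.56) = 29%

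**4. Effect on the moderators.** A guideline shift of equal size for every provider moves all scores together and leaves the interaction slope alone. A shift from CDS training moves scores in one arm only, so the moderator then partly measures the arm.

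**5. How many providers?** The Protocol Summary allows up to 88 dentists and 88 hygienists in private practices: 88 + 88 = 176. This is a ceiling across both arms. It includes control providers, who receive no CDS training, and anyone who answers at enrollment.

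**The case against.** The strongest reply is that the end of training is a deadline and enrollment is the planned time. That is a fair reading of 8.1 and 7.2, and some surveys will have been returned early. Their share is unknown, however, and the rule accepts the rest.

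The reply also limits what may be claimed:
- A reader might infer that every private-practice provider knows the arm when answering. The documents do not give the order of randomization, survey and training in that setting.
- A reader might infer that the contamination is certainly one-sided. The training session is not defined, and section 4 describes the CDS training as limited and technical. Training detail is left to the Manual of Procedures (section 6.7), which is not available here.
- A reader might put the loss of mediator signal at the full share of the gain made in training, for all 176 providers. That assumes everyone answers late and treats within-arm change as the signal. Mediation of the CDS effect rests on the between-arm contrast, from which equal guideline training drops out.
- A reader might object that school and private-practice results for Objective 4 are not comparable. All analyses are run separately by setting, and no cross-setting comparison is planned.

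The consequence is also modest. Objective 4 is exploratory. Section 3.1 names only mediators, although the Protocol Summary and Table 2 keep moderators. The SAP covers Objectives 1 to 3 and excludes analyses of effect heterogeneity in them. Finally, the SAP is dated April 2022 and describes limited private-practice survey counts, so much baseline collection may be past. All of this stands and lowers the severity. It does not remove the permission in 8.1.

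**Conclusion.** The point holds as a matter of what the protocol permits. A compliant private-practice baseline TDQ may be completed during or after training. Whether the resulting error differs by arm depends on whether the training session includes the CDS component, which is a reasonable reading of the Protocol Summary but is not stated.

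The effect is confined to Objective 4 in private practices. Its size cannot be determined from the documents: the factor 1 − s·f rests on two unknown shares, and the assumed cases in the working run from a small loss to a complete one. The patient-reported endpoints of Objectives 1 to 3 do not use provider baseline scores and are untouched. Severity is low to moderate.

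**What to change.** **Wording.** Change the private-practice sentence in 8.1 so that providers complete and return the baseline survey before any training content and, where feasible, before the clinic's arm is disclosed. State what the training session consists of.

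**Dates.** Record the survey date and each training date against the study ID that already links the two provider surveys, since 8.1 collects responses apart from other identifiers.

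**Surveys already collected.** Recover those dates where possible. Run Objective 4 with a sensitivity analysis that excludes baselines dated on or after training. If dates cannot be recovered, report the uncertain timing as a limitation.

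**Cost.** One revised sentence, two recorded dates, and a reminder before training opens. A few late surveys are lost as baselines, which matters somewhat because the private-practice sample may be small; for surveys already collected, the exclusion is therefore a sensitivity analysis and not the main one.
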